1.0 Objectives

1.1 Study Objectives

The main objective is to compare the test characteristics of the human papillomavirus (HPV) self-sampling kit versus clinician-sampled HPV testing for cervical cancer screening. This study seeks to find out if the HPV self-sampling kit is non-inferior to standard clinician-sampling practices.

1.2 Primary Study Endpoints

The primary outcomes of this study are to analyze the screening results on self-sampling kits compared to clinician-collected HPV test, Pap smear results, and colposcopy.

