3.0 Inclusion and Exclusion Criteria

3.1 Inclusion Criteria

1. Ages 30-65 years
2. Penn State Health (PSH) patient
3. Female
4. Has an intact cervix
5. With abnormal findings on Pap/HPV test that requires a colposcopy for follow-up
6. Speaks, reads, or writes well in English or Spanish

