6.2 Waiver or Alteration of Authorization for the Uses and Disclosures of PHI

6.2. 1 Access, use or disclosure of PHI representing no more than a minimal risk to the privacy of the individual

6.2 .1.1 Plan to protect PHI from improper use or disclosure

Information is included in the “Confidentiality, Privacy, and Data Management” section of this protocol.

6.2 .1.2 Plan to destroy identifiers or a justification for retaining identifiers

Protected health information (PHI) will be used for recruitment through the EMR by members of the study team. All EMR data and study data will be input into REDCap (i.e., insurance status, and date and results of previous Pap/HPV tests). There will be two databases for participant data. The first linking list will contain the medical record number (MRN) and the unique study ID number. This list will be destroyed after data collection. The second linking list will have the study ID with all study data. This second linking list will be kept for up to two years after data collection.

Identifiers will be destroyed after the completion of data analysis.

6.2. 2 Explanation for why the research could not practically be conducted without access to and use of PHI

The proposed study requires enrollment of participants who have abnormal findings on Pap/HPV tests to compare those results with the findings from a self-sampled HPV test. Identification of these participants would be infeasible using other methods.

6.2. 3 Explanation for why the research could not practically be conducted without the waiver or alteration of authorization

Prospective identification of participants with abnormal findings on Pap/HPV tests using PHI prior to consent will be more practical and efficient than obtaining consent prior to determining whether a potential participant had abnormal findings on these tests.

Having participants provide implied consent by using the Summary Explanation of Research is more practical because it allows the study team to send a kit to participants prior to their appointment, and therefore gives the participant more time to complete study procedures. This process also makes it easier to participate in the study since all materials are mailed to the participants home, and they will not take up any extra clinic time during their appointment.

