Participants must complete the self-sampling kit within 14 days before or after their colposcopy visit, meaning that there is a 28 day window for participants to collect the sample. A 2nd HPV self-sampling kit will only be mailed if the participant states that she lost or did not receive the first one. Participants will receive a maximum of 2 HPV self-sampling kits.

Once the HPV self-sampling kit has been returned and the survey completed, the study participants will be mailed an incentive in the form of a Greenphire ClinCard, and a thank you letter from the PI. Analysis of the self-sampling specimens will be conducted to determine HPV DNA positivity to compare to the results of the previous Pap test, HPV test, and colposcopy. EMR data will be used to check insurance status, and the date and result of Pap test, HPV test, and colposcopy.

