8.3 Statistical methods

We will conduct Fisher's exact tests to examine our primary study outcome, i.e., concordance/non-inferiority of HPV self-sampling test results versus clinician-sampled test results. Additional analyses of the concordance across test will use Cohen's kappa coefficient. In addition, we will summarize survey results using descriptive analysis, including calculating means, Pearson's correlation coefficients, and Fisher's exact tests.

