11.2 Potential Benefits to Others

Understanding how the results of the HPV self-sampling kit compare to clinician-collected HPV tests, Pap smears, and colposcopies will ultimately help to create a better screening process. If the findings are similar across tests, HPV self-sampling may emerge as an effective option for cervical cancer screening among underserved populations without routine access to preventive healthcare.

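### Agreement with the Pap smear cannot count for or against the self-sample: in women referred for an abnormal Pap/HPV result, an exact copy of the clinician HPV result would score a kappa of at most 0 against Pap

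*Combined protocol and SAP*

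**What the plan says.** Section 1.2 describes the primary outcomes as "the screening results on self-sampling kits compared to clinician-collected HPV test, Pap smear results, and colposcopy", with no ranking among the three comparators. Section 7.1 makes the self-sample result binary, since the specimens are analysed to "determine HPV DNA positivity to compare to the results of the previous Pap test, HPV test, and colposcopy".

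The statistical section is worded differently. Section 8.3 takes the primary outcome to be "concordance/non-inferiority of HPV self-sampling test results versus clinician-sampled test results", tested with Fisher's exact test, and then adds: "Additional analyses of the concordance across test will use Cohen's kappa coefficient". It does not say which pairs of tests the kappa covers, and it does not exclude Pap. Section 1.1 is narrower still: it names clinician-sampled HPV testing as the comparator.

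On entry, section 3.1 requires women "With abnormal findings on Pap/HPV test that requires a colposcopy for follow-up". Section 6.2 confirms that the selecting results are also the comparison results, because the study "requires enrollment of participants who have abnormal findings on Pap/HPV tests to compare those results with the findings from a self-sampled HPV test". Section 11.2 names Pap smears among the comparators and continues: "If the findings are similar across tests, HPV self-sampling may emerge as an effective option for cervical cancer screening among underserved populations".

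**The concern.** Cytology and an HPV DNA test measure different things. A woman who is HPV-positive with a normal Pap is not an error of the self-sample. She is a woman in whom the two tests differ, however the HPV specimen was collected. Kappa against Pap counts her as a disagreement all the same.

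The entry rule makes this worse. Women normal on both tests are not referred, so the cell in which HPV and Pap would agree on a negative result is removed by design. What remains is joint positives plus the women in whom the two tests differ. In such a table a faithful self-sample looks discordant with Pap, and one that loses HPV infections in Pap-normal women looks more concordant. A reader who takes similarity across tests as support, as section 11.2 invites, could be led the wrong way.

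**Working it through.** **The plan's own figures.** The documents give no expected or target kappa for any pair of tests, so there is no kappa figure to reproduce. Section 8.2 gives 30 participants but no target kappa, expected rates, margin or sidedness, so that number cannot be reproduced either. It is used below only as the table total.

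**Set-up.** Take 30 women with both a Pap and a clinician HPV result. Cells: a = HPV+/Pap abnormal, b = HPV+/Pap normal, c = HPV-/Pap abnormal, d = HPV-/Pap normal. If either abnormal result qualifies (section 3.1) and Pap is split at the referral threshold, then d = 0. Suppose first that the self-sample equals the clinician HPV result in every woman. The self-sample/Pap table is then this same table.

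**Formula.** kappa = 2(ad - bc) / [(a+b)(b+d) + (a+c)(c+d)]. With d = 0 the numerator is -2bc, which is never positive.

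**All splits.** There are 32 × 31 / 2 = 496 tables with a + b + c = 30 and d = 0. None has kappa above 0. In 60 it is exactly 0 (only one of b and c is non-zero), in 435 it is negative, and in 1 it is undefined (all 30 positive on both tests).

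**Assumed splits, self-sample a perfect copy:**

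| a/b/c/d | Observed agreement | Chance agreement | kappa |
|---|---|---|---|
| 22/4/4/0 | 22/30 = 0.733 | (26×26 + 4×4)/900 = 0.769 | -0.15 |
| 18/7/5/0 | 18/30 = 0.600 | (25×23 + 5×7)/900 = 0.678 | -0.24 |
| 14/10/6/0 | 14/30 = 0.467 | (24×20 + 6×10)/900 = 0.600 | -0.33 |

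**Making the self-sample worse.** Start from an assumed 18/8/4/0, in which 18 + 8 = 26 women are clinician HPV-positive. Let the self-sample be negative in m of the 8 HPV-positive, Pap-normal women. Those women move from b to d.

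| m | Self-sample/Pap table | Clinician HPV-positives detected | kappa against Pap |
|---|---|---|---|
| 0 | 18/8/4/0 | 26/26 = 100% | -0.22 |
| 2 | 18/6/4/2 | 24/26 = 92% | 0.07 |
| 4 | 18/4/4/4 | 22/26 = 85% | 0.32 |
| 8 | 18/0/4/8 | 18/26 = 69% | 0.71 |

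For m = 8: observed agreement is 26/30 = 0.867, chance agreement is (18×22 + 12×8)/900 = 0.547, and kappa = 0.320/0.453 = 0.71. Detection falls while agreement with Pap rises.

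**Fisher's exact test.** With d = 0 the sample odds ratio ad/(bc) is 0 whenever b and c are both non-zero, so any association is inverse. At an assumed 10/15/5/0 the p-value is 0.042. Read as concordance, that significant result would mean the opposite of what it shows.

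**The case against.** The strongest reply is that the plan never commits to kappa against Pap as a primary analysis. Section 1.2 speaks of comparing, not agreeing. Sections 1.1 and 8.2 concern two ways of obtaining the result, and section 8.3 makes Fisher's test primary and kappa additional. That is right, and a reader who inferred a primary Pap kappa would be joining section 1.2's list to a loose phrase in section 8.3. What remains is that section 1.2 does make Pap a primary comparator, section 8.3 does not exclude it from kappa, and a Pap smear is itself a clinician-sampled test.

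A reader might also infer that the trial's observed self-sample/Pap kappa must be 0 or below. The documents do not support this. The self-sample is a new specimen taken around colposcopy and compared with earlier tests, so a Pap-normal woman can be self-sample negative, including through real change since referral. The bound applies to a perfect copy, and only under the stated conditions. Section 3.1 does not require both tests. No Pap cut-off is defined, and a stricter one could refill the empty cell: moving 2 of the 4 HPV-negative, Pap-abnormal women in 18/8/4/0 gives 18/8/2/2 and kappa 0.12. If entry required both results to be abnormal, a perfect copy would give an undefined kappa, which is no more informative.

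Finally, one might infer that a good self-sample would formally fail. It would not: the plan sets no kappa threshold, and section 11.2 is a statement of potential benefit, not a decision rule.

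**Conclusion.** The point holds as a defect of interpretation and of consistency between sections. Among women with both tests, with either abnormal result qualifying and Pap split at the referral threshold, a self-sample identical to the clinician HPV result has kappa of at most 0 against Pap. That bound is algebra. The individual values (-0.15 to -0.33 for a perfect copy, and the rise from -0.22 to 0.71 as infections are missed) rest on assumed splits of 30 women. Where the conditions are relaxed the bound goes, but a high or low Pap kappa still says nothing dependable about collection method. Fisher's test against Pap has the same weakness. The self-sample versus clinician HPV comparison, which answers the objective in section 1.1, is not affected by this point, so correcting the Pap comparison before analysis is worthwhile but does not decide the study's value.

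**What to change.** - **Sections 1.1, 1.2 and 8.3:** reconcile them so that self-sample versus clinician-collected HPV test is the primary concordance comparison.
- **Section 8.3:** state that kappa and Fisher's exact test are not used as concordance measures against Pap. Instead, within each Pap category, report self-sample and clinician HPV positivity side by side in the same women, so that only the difference between collection methods is interpreted.
- **Section 11.2:** reword so that similarity refers to the clinician-collected HPV test.
- **Colposcopy:** leave this comparison in place as a separate analysis.

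The cost is wording in these sections, with no new patients, specimens or data, and one fewer headline comparison. Counts within Pap categories will be small with 30 completers, so that table is descriptive. The change does not remove the selection problem in the HPV-HPV comparison, which is still made in women chosen for abnormal results.

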1.3 Secondary Study Endpoints

Secondary endpoints will include acceptability of self-sampling and barriers to cervical cancer screening. These endpoints will be analyzed to try to circumvent barriers to the cervical cancer screening and ascertain whether self-sampling is a viable alternative.

2.0 Background

2.1 Scientific Background and Gaps

The American Cancer Society estimates that 4,170 women in the United States (US) will die from cervical cancer in 2018.¹ Screening can reduce cancer mortality by (1) detecting malignancies when they are more treatable² and (2) for some tests, identifying precancerous lesions for removal. Guidelines recommend cytology and/or HPV testing for cervical cancer screening among women ages 30-65 years, but screening rates are suboptimal.^{3,4}

To help bridge these gaps in screening, HPV self-sampling would be an alternative to clinical screening. However, there are concerns about the efficacy and comparability of self-sampling kits as an effective tool to detect cervical cancer.

2.2 Previous Data

There have been previous studies about the effectiveness of self-collected samples as an alternative to clinician collected samples. Some studies state that HPV testing is more sensitive than Pap testing.⁵ There is a possibility that these two samples have similar sensitivity.⁶ Based on this information, examining test characteristics and acceptability of each technique is necessary to support larger efforts to make self-sampling available.

2.3 Study Rationale

The impact of the proposed project is to compare HPV self-screening results with Pap smear results, clinician-collected HPV test, and colposcopy to ultimately improve the uptake of HPV screening.

3.0 Inclusion and Exclusion Criteria

3.1 Inclusion Criteria

1. Ages 30-65 years
2. Penn State Health (PSH) patient
3. Female
4. Has an intact cervix
5. With abnormal findings on Pap/HPV test that requires a colposcopy for follow-up
6. Speaks, reads, or writes well in English or Spanish

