7.0 Study Design and Procedures

7.1 Study Design

After the participant is screened and informs the study team member that they would like to enroll in the study, an HPV self-sampling kit, the instructions on how to use it, a summary explanation of research, PSH lab Pathology Services Special Account Requisition form, and a letter from the principal investigator (PI) (see "[name] Self-sampling Letter") will be mailed to study participants. Participants will be asked to complete the HPV self-sampling kit within a week. 3-5 days before the colposcopy appointment a study team member will reach out to check if study participants have completed their HPV self-sampling kit. Those that have completed the kit will complete a survey (HPVSelSamplingAcceptabilityAn) over the phone and get an appointment reminder. They will mail their HPV self-sampling kit and PSH lab Pathology Services Special Account Requisition form to the lab. On the day of their appointment, their clinician will perform a colposcopy following normal clinical procedures.

Participants who have not completed their HPV self-sampling kit will get instructions not to use the HPV self-sampling kit before the colposcopy and get an appointment reminder. They will then go to their appointment where the clinician will perform the colposcopy. After their visit, the participant will receive a reminder to use the HPV self-sampling kit within two weeks. The participant will receive a maximum of three phone calls after their colposcopy appointment to remind them to return their completed self-sampling kit. Seven days after the colposcopy appointment the research project manager will call the participant to determine if she completed the HPV self-sampling kit and, if so, they will complete a survey (HPVSelSamplingAcceptabilityAn) over the phone. If the participant has not completed the kit or does not respond, a second phone call will then occur 10 days after the colposcopy appointment. A final phone call will up to 21 days after the colposcopy appointment. If the self-sampling kit is not collected 21 days after the colposcopy or if the study team is unable to reach the participant, their participation will be considered incomplete.

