7.2 Study Procedures

Survey and HPV self-sampling kit

7.2. 1 Up to 21 days before the colposcopy appointment

A study team member will obtain implied verbal consent from the participants and mail the HPV self-sampling kit with the instructions, a summary explanation of research, PSH lab Pathology Services Special Account Requisition form, and [name] Self-sampling Letter.

7.2. 2 3-5 days before the colposcopy appointment

A study team member will call study participants to provide a reminder to attend their colposcopy appointment and, if they completed their HPV self-sampling kit, take a survey (HPVSelfSamplingAcceptabilityAn) over the phone. Those that did not complete the HPV self-sampling kit will get an appointment reminder and be told not to use the self-sampling kit before the colposcopy.

7.2. 3 Up to 21 days after colposcopy appointment

Seven days after their colposcopy visit, a study team member will call those participants who did not complete the HPV self-sampling kit prior to the colposcopy appointment to complete a survey (HPVSelfSamplingAcceptabilityAn) over the phone. If they still have not completed the HPV self-sampling kit, they will be reminded to complete the self-sampling kit and a study team member will schedule another phone call to complete the survey (HPVSelfSamplingAcceptabilityAn) up to 21 days post-colposcopy. Once the HPV self-sampling kit has been returned and the survey completed, the study team will mail out the participant's incentive and the Thank You Letter. If the participant did not complete the kit then no further contact will be made after day 21, and the participant will not receive a gift card nor will they be included in the goal of 30 total completers.

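### The abnormal Pap/HPV result that admits a woman is also the clinician comparator, so the planned concordance/non-inferiority result depends on the entry mix, and no clinician HPV result is required

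*Combined protocol and SAP*

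**What the plan says.** - **Entry (3.1).** A woman qualifies "With abnormal findings on Pap/HPV test that requires a colposcopy for follow-up". The criterion does not say that an HPV result must exist, and it sets no limit on the age of the result.
- **Comparator (6.2.2, 7.1).** Section 6.2.2 says the study needs "enrollment of participants who have abnormal findings on Pap/HPV tests to compare those results with the findings from a self-sampled HPV test". Section 7.1 says the self-sample is analysed for "HPV DNA positivity to compare to the results of the previous Pap test, HPV test, and colposcopy".
- **The visit (7.1).** "On the day of their appointment, their clinician will perform a colposcopy following normal clinical procedures". Neither 7.1 nor 7.2 describes a clinician HPV sample taken for the study.
- **Dates.** "EMR data will be used to check insurance status, and the date and result of Pap test, HPV test, and colposcopy". Under 7.4.6.3 the participant writes the date and time of self-collection on the requisition form. No analysis uses either date.
- **Timing.** "Participants must complete the self-sampling kit within 14 days before or after their colposcopy visit". This window is counted from the colposcopy, not from the clinician HPV sample.
- **Analysis (1.1, 8.2, 8.3).** The objective is non-inferiority to clinician sampling. Section 8.2 says 30 participants suffice for concordance/non-inferiority. Section 8.3 uses Fisher's exact test for the primary comparison of self-sampled with clinician-sampled results, and kappa in addition.

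**The concern.** The two tests are not treated alike. The clinician result decides who is in the study; the self-sample does not. Summaries that mix clinician-positive and clinician-negative women therefore describe the referral mix as well as the kit. Two equally accurate tests can appear to differ in overall positivity, and a good overall figure can say little about women the clinician test called negative.

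Two gaps add to this. The entry criterion can be met by an abnormal Pap alone, so one of the 30 completers may have no clinician HPV result to pair. And the clinician sample precedes the self-sample by an interval that no rule limits, during which an infection may clear.

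At stake is whether 8.3, applied as written, yields a non-inferiority statement that the design cannot carry.

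**Working it through.** **Inputs from the plan.** 30 completers (8.2); at least 18 potentially eligible patients a month and 120 invitations (15.2). The plan gives no margin, expected agreement, kappa, share of clinician-positive women or share with a clinician HPV result. The 30 therefore cannot be reproduced from its own inputs, and every accuracy or share figure below is an assumption. The recruitment figure does reproduce: 120/18 = 6.7, which the plan gives as about 7 months.

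**1. Positive agreement and selection.** Assume 20% infected, both tests 95% sensitive and 95% specific with independent errors, and no elapsed time.
- Clinician-positive: 0.20×0.95 + 0.80×0.05 = 0.230.
- Both positive: 0.20×0.95² + 0.80×0.05² = 0.1825.
- Positive agreement: 0.1825/0.230 = 79.3%.

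This already conditions on a positive clinician result, so enrolling every clinician-positive woman leaves it at 79.3%. If entry also needs an abnormal Pap, false positives are filtered out and it rises, at most to 0.1805/0.19 = 95% if the Pap removed them all.

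**2. Overall positivity.** Let p be the clinician-positive share among entrants, PA positive agreement and NA negative agreement.
- Self-positive share = p×PA + (1−p)×(1−NA).
- Unselected women: both negative = 0.20×0.05² + 0.80×0.95² = 0.7225; NA = 0.7225/0.77 = 93.8%. Self-positive = 0.23×0.793 + 0.77×0.062 = 0.23, equal to the clinician share, as it should be.
- Entrants, p = 0.74 assumed: 0.74×0.793 = 0.587. With NA = 93.8%, add 0.26×0.062 = 0.016, giving 60%. With NA = 84.6% (lower because negatives enter only through an abnormal Pap; the value rests on assumed Pap performance), add 0.26×0.154 = 0.040, giving 63%.

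Two equally accurate tests thus show 74% against 60–63% positive.

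**3. Elapsed time.** If every clinician-positive woman was truly infected, detection is 95% and cleared infections test negative, positive agreement is 0.95×(1−share cleared): 95%, 85.5% and 76% at 0, 10% and 20% cleared. The true share is not known.

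**4. Number of negatives and kappa.** With 30 pairs and 90% agreement in both groups: q = 0.9p + 0.1(1−p), pe = pq + (1−p)(1−q), kappa = (0.9−pe)/(1−pe).

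| Clinician-positive share | Expected negatives | Chance of 2 or fewer | Kappa |
|---|---|---|---|
| 50% | 15 | <0.1% | 0.80 |
| 80% | 6 | 4% | 0.72 |
| 90% | 3 | 41% | 0.59 |
| 95% | 1.5 | 81% | 0.43 |

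Agreement is the same in every row; only the case mix moves kappa. Perfect negative agreement has an exact 95% CI of 54–100% for 6/6 and 29–100% for 3/3.

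**5. What Fisher's test can conclude.** Suppose 14 of 24 clinician-positive and 6 of 6 clinician-negative women agree. Fisher's test on that cross-table gives p = [C(16,6) + C(14,6)]/C(30,6) = (8008 + 3003)/593775 = 0.019. The result is significant, yet positive agreement is 14/24 = 58%. The test detects association, which is not non-inferiority.

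**6. Pairs.** If 0–30% of completers lack a clinician HPV result, 30 down to 30×0.7 = 21 pairs remain.

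**The case against.** **Enrolling women with abnormal results is deliberate.** Section 6.2.2 explains the choice, and the title of reference 6 describes a paired screen-positive non-inferiority trial. This stands: screen-positive entry is not itself a defect. What is at issue is the conclusion drawn from it.

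**Selection does not bias positive agreement.** A reader might infer that women who enter on a clinician false positive push positive agreement down because of the entry rule. The documents do not support that. A clinician false positive counts as a disagreement in an unselected paired study too, and step 1 shows no change. If referral also depends on the Pap, selection could raise it. Only clearance over time clearly lowers it.

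**The comparator need not be all HPV-positive.** A reader might infer that kappa collapses to zero. That would require every entrant to be clinician-positive, whereas 3.1 also admits HPV-negative women with an abnormal Pap.

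**A clinician HPV result seems expected, and follow-up keeps the interval short.** Section 7.1 names the previous HPV test among the comparators, and 15.2 speaks of completing all study procedures. A Pap-only completer still informs the Pap and colposcopy comparisons in 1.2. Follow-up of an abnormal result limits its age in practice, and its date is collected. These points reduce the likely size of the problem. Still, no rule secures the pair, and no analysis reports the interval.

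**Conclusion.** The point holds as a reporting and eligibility problem that should be fixed. It does not invalidate the study. That the entry result is also the comparator follows directly from 3.1, 6.2.2 and 7.1, and confidence in this is high. The consequence is that an overall agreement, kappa, positivity or non-inferiority statement reflects the entry mix, with the positivity contrast tilted against self-sampling. Negative agreement may rest on a handful of women selected by Pap.

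Confidence in any size is low. The 74% against 60–63% contrast, the 3 expected negatives and the 21–30 pairs all rest on shares and accuracies that the documents do not give. The net direction of bias in positive agreement is not established: clearance lowers it, and entry that also needs an abnormal Pap could raise it.

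**What to change.** 1. **Secure the pair.** In 3.1, or in the definition of the 30 completers in 7.2.3, require a clinician HPV result on record, checked in the EMR review already planned in 4.1.
2. **Change the clinician-HPV analysis in 8.3.** Replace the Fisher-based concordance/non-inferiority test with positive and negative agreement reported separately, with counts and exact 95% CIs. Keep kappa as description. Limit conclusions to referred women. State that elapsed time can lower positive agreement, and that selection on the clinician result prevents an overall non-inferiority or specificity conclusion. Align 1.1 and 8.2 with the expected precision, for example 22/24: 73–99% and 6/6: 54–100%.
3. **Report the interval** between the clinician HPV sample and the self-sample, from the EMR and requisition dates.

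As a separate minor point, the 14-day window in 7.1 should be reconciled with the day-21 passages: "If the self-sampling kit is not collected 21 days after the colposcopy" in 7.1, "no further contact will be made after day 21" in 7.2.3, and consent up to 21 days after colposcopy in 5.2.1.

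**Cost.** No extra visit, sample or data item is needed. The text changes do give up the overall non-inferiority claim in 1.1, which is a real narrowing of the main objective. If 10–30% of otherwise eligible women lack a clinician HPV result (assumption), the same yield needs 120/0.9 = 133 to 120/0.7 = 171 invitations, or 7.4 to 9.5 months at 18 a month, against 6.7 now. If none lack one, there is no recruitment cost. These steps disclose the dependence on the entry mix; they do not remove it.
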